### 3.5.3 Physical & Skin Examination

A complete physical examination will be conducted at Visit 1 and at Visit 7. At other visits, an abbreviated examination will be performed. While the findings from the physical examination will not be captured on the eCRF, nor analyzed directly, changes from baseline in any physical examination findings identified by the Investigator as clinically significant (CS) will be recorded as an adverse event. Additionally, changes in sexual function, for both males and females, will be assessed at each visit. Changes in male sexual function include:

- Change in:
  - Erections
    - Ability to achieve
    - Ability to maintain
    - Change in frequency
    - Change in timing
    - Other
  - Ejaculations
    - Early occurring
    - Difficulty
    - Pain
    - Other
  - Sex drive
    - Increased
    - Decreased
  - Other
- If change is still occurring (Yes, No)

Changes in female sexual function include:

- Change in:

- Vagina engorgement
  - Clitoral sensitivity
  - Sex drive
  - Other
- If change is still occurring (Yes, No)
- If change is:
  - Sexual
  - Non-sexual
  - Painful

For patients that have not reached Tanner Stage V, Tanner staging (Stage I, Stage II, Stage III, Stage IV, Stage V, and Not Applicable) for assessment of pubertal development will also be conducted at each visit.

A comprehensive skin examination will also be performed at Visit 1 and Visit 6. Normal and abnormal findings regarding skin lesions will be assessed. At each visit skin hyperpigmentation, changes in skin tone, new mole development, and changes in existing moles will be assessed.

### **3.5.4    ECG**

A single 12-lead ECG recording will be done at: Visit 1, Visit 2 (before and after treatment), Visit 3 and Visit 6. The following items will be measured:

- Heart rate (HR) (beats/min)
- PR interval (msec)
- QRS interval (msec)
- QT interval (msec)
- QTcF interval (msec)
- Overall Interpretation (Normal, Abnormal – Not Clinically Significant, Abnormal – CS)

### **3.5.5    Clinical Laboratory Tests**

Hematology, clinical chemistry, and urine analysis laboratory tests will be performed at every visit. HbA1c is only collected at Visit 1 and Visit 6; [REDACTED] is only performed at Visits 2, 6, and 7. At each applicable visit, the laboratory tests will be collected prior to study treatment.

### **3.5.6 Injection Site Examination**

At each visit where study treatment is administered (every visit starting at Visit 2) the injection site will be evaluated. The injection site evaluation will include:

- Reaction (Erythema, Edema, Induration, Itching, Pain or Tenderness, Other)
  - Length (Erythema, Edema, Induration only)
  - Width (Erythema, Edema, Induration only)
- Finding (None, Mild, Moderate, Severe)
- Clinically significant (Yes, No)

### 3.5.7 Global Hunger Questionnaire

■ . Depending on the age of the patient, 1 of 2 versions of the Global Hunger Questionnaire will be administered. For patients less than 12 years of age, the patient's parent/caregiver will complete the questionnaire; for patients 12 years of age or older, the patient will complete the questionnaire themselves.

The Global Hunger Questionnaire will be performed at every visit starting at Visit 2 and will be completed prior to study treatment administration.

### 3.5.8 Daily Hunger Questionnaire

The Daily Hunger Questionnaire is a questionnaire that will be completed every day, starting at Visit 1, used to assess patient's own hunger. The questionnaire will be completed prior to the morning meal and prior to study treatment each day in the morning.

### 3.5.9 Impact of Weight on Quality of Life-Lite Clinical Trials (IWQOL-Lite-CT)

The IWQOL-Lite-CT is a validated 20-item self-report measure of obesity-specific quality of life questionnaire. The IWQOL-Lite-CT yields a Total score and 3 composite scores: Physical (7 items), Physical Function (5 items) and Psychosocial (13 items). Each item has 5 possible scaled responses: 1 – Never/Not at all true; 2 – Rarely/A little true; 3 – Sometimes/Moderately true; 4 – Usually/Mostly true; 5 – Always/Completely true,

where lower item scores indicate higher levels of functioning. Only patients 18 years of age or older will complete the IWQOL-Lite-CT. Patients will complete the IWQOL-Lite-CT at: Visits 1, 2, 3, and 6. For each post-baseline visit, the IWQOL-Lite-CT will be completed prior to study treatment administration.

### Scoring Methods

- Physical Score: Includes Items 1-5, 16, 17
- Physical Function Score: Includes Items 1-3, 16, 17
- Psychosocial Score: Includes Items 6-15, 18-20
- Total Score: Includes all Items (1-20)

For each score listed above, if the minimum number of items is answered for a composite (see below), the non-missing item responses are averaged to compute the raw composite score. The composite score is then calculated by transforming the raw composite score to the 0 (worst)-to-100 (best) metric using the following formula for every patient at each time point:

$$100 (5 - C_{avg})/4.$$

where:

$C_{avg}$  is the raw average score of all non-missing item responses in the composite; this average must be a number between 1 and 5, inclusive.

### Missing data rules

The 3 composite scores can be computed if a minimum of 50% of the items for each composite are non-missing. The total score requires 75% of all items to be non-missing. This equates to the following:

- Physical: 4 of 7 items non-missing
- Physical function: 3 of 5 items non-missing
- Psychosocial: 7 of 13 items non-missing
- Total: 15 of 20 items non-missing

### **3.5.10 Patient Health Questionnaire (PHQ)**

There are 2 versions of the Patient Health Questionnaire used depending on the age of the patient. Patients age 6 – 10 will not complete any version of the PHQ; patients 11-17 years of age will complete the PHQ-A; patients 18 years of age or older will complete the PHQ-9.

The PHQ-9 is a 9-item depression scale of the Patient Health Questionnaire. The PHQ-9 is a tool for assisting clinicians in diagnosing depression as well as selecting and

monitoring treatment. The PHQ-9 yields a Total Score and consists of 10 items. Each item has 4 possible scaled responses. The PHQ-A is a modification of the PHQ-9 for adolescents. The PHQ-A also yields a Total Score and consists of 13 items. Each item has 4 possible scaled responses (Kroenke et al., 2001).

Patients will complete the PHQ-9/PHQ-A at every study visit. For each post-baseline visit, the PHQ-9/PHQ-A will be completed prior to study treatment administration.

#### Scoring Methods

- PHQ-9 Total Score: Calculated as the sum of: PHQ1 – PHQ9 (9 items). A higher total score indicates higher risk of depression.
- PHQ-A Total Score: Calculated as the sum of: PHQA1 – PHQA9 (9 items). A higher total score indicates higher risk of depression.

#### **3.5.11 Columbia-Suicide Severity Rating Scale (C-SSRS)**

There are 2 types of the C-SSRS used depending on the age of the patient. Patients age 6 – 11 will complete the Children C-SSRS type; patients 11 years of age and older will complete the Adult C-SSRS type.

The C-SSRS is a tool used not only to predict suicide attempts but to assess the full range of evidence-based ideation and behavior items, with criteria for next steps. All patients will complete 2 versions of the C-SSRS throughout the study:

1. The Baseline/Screening version of the scale combines the Baseline and Screening forms to assess suicidality in a patient's lifetime and during a predefined time. This version can assess a patient's lifetime suicidality for data collection purposes.
2. The Since Last Visit version of the scale assesses suicidality since the patient's last visit. This version is meant to assess patients who have completed at least one initial C-SSRS assessment and should be used in every subsequent (post-baseline) visit. The 'Since Last Visit' version of the C-SSRS is asking about any suicidal thoughts or behaviors the patient/participant may have had since the last time the C-SSRS was administered.

Patients will complete the C-SSRS at every study visit. For each post-baseline visit, the C-SSRS will be completed prior to study treatment administration.

#### **3.5.12 Short Form (SF)**

There are 2 versions of the Short Form Questionnaire used depending on the age of the patient. Patients less than 18 years of age will not complete the SF-10; rather their parent/caregiver will complete the questionnaire; patients 18 years of age or older will complete the SF-12.

The SF-12 is a self-reported outcome measure assessing the impact of health on an individual's everyday life that is often used as a quality of life measure. It is a 12-item shortened form of the 36-item SF-36 that can be completed either by the patient or through interview. The SF-10 is a modified 10-item questionnaire that is to be completed by caregivers rather than the patient. The scoring method yields two summary measures: a physical summary score and a psychosocial summary score.

Patients/caregivers will complete the SF-12/SF-10 at Visits 1, 2, 3, and 6. For each post-baseline visit, the SF-10/SF-12 will be completed prior to study treatment administration.

The SF-10 and SF-12 summary scores will be calculated following the manuals for the handling of the data (scoring, transformations, missing values, etc.).

### **3.5.13 EuroQol- Five Dimension (EQ-5D)**

There are 2 versions of the EQ-5D used depending on the age of the patient. Patients between 6 and 8 years of age will not complete any version of the EQ-5D; patients 8 -16 years of age will complete the EQ-5D-Y; patients 16 years of age or older will complete the EQ-5D-5L.

The EQ-5D-Y is a standardized instrument to measure health-related quality of life that can be used in a wide range of health conditions and treatments. It is the child-friendly version of the EQ-5D. The EQ-5D-Y consists of a descriptive system and the EQ VAS. The EQ-5D-Y descriptive system comprises the following five dimensions: mobility, looking after myself, doing usual activities, having pain or discomfort and feeling worried, sad or unhappy. Each dimension is rated on a 3-point response scale indicating: 1 - no problems, 2 - some problems, and 3 - a lot of problems. The EQ VAS records the patient's self-rated health on a vertical visual analogue scale where the endpoints are labelled "The best health you can imagine" and "The worst health you can imagine". The VAS can be used as a quantitative measure of health outcome that reflects the patient's own judgement (EuroQol, 2021).

The EQ-5D-5L is a standardized measure of health status comprised of a descriptive system including five health-related quality of life states (i.e., mobility, self-care, usual activities, pain/discomfort, and anxiety/depression) and a VAS of overall health. Each dimension is rated on a 5-point response scale indicating severity of problems, where 1 is "no problems" and 5 is "extreme problems". The EQ VAS records the patient's self-rated health on a vertical visual analogue scale, where the endpoints are labelled 'The best health you can imagine' and 'The worst health you can imagine'. The VAS can be used as a quantitative measure of health outcome that reflect the patient's own judgement (EuroQol, 2021).

Patients will complete the EQ-5D-Y/EQ-5D-5L at Visits 1, 2, 3, and 6. For each post-baseline visit, the EQ-5D-Y/EQ-5D-5L will be completed prior to study treatment administration.

## 4 General Analysis Conventions

All tables, listings, and figures will be programmed using SAS Version 9.4 or higher. Data collected in this study will be documented using summary tables and patient data listings created by using the SAS® system. Confidence intervals (CI) will be performed at a significance level of 5%, unless otherwise specified. Data for all patients in the clinical database will be included in the data listings. Calculated (derived) variables will be listed as appropriate.

All efficacy, safety and baseline characteristics variables will be presented using descriptive statistics and figures as appropriate. Continuous variables will be summarized using descriptive statistics (number of observations, mean, standard deviation (SD), median, minimum, and maximum). Categorical variables will be presented in frequency tables with number and percent of observations for each level. Missing counts for all variables will be presented for informational purposes only and will not be included in percentage calculations.

Study days will be calculated relative to the first injection of study drug. Day 1 will be the first day of study drug administration in the study. In data listings, the relative study day (in relation to date of first study drug administration) of all dates will be presented.

Adverse events, medical history events, and concomitant treatments/procedures will be coded using Medical Dictionary for Regulatory Activities (MedDRA), Version 24.0 or higher. Prior/concomitant medications will be coded using the World Health Organization (WHO) Drug Dictionary Global B3, March 2021 or higher.

Any changes from the SAP will be detailed in the Clinical Study Report (CSR).

### 4.1 Study Periods

The study has two periods: Screening and Treatment.

- Screening Period – From providing informed consent to just before Baseline Visit (Visit 2). Can range between 56 – 14 days prior to Visit 2.
- Treatment Period - From the Baseline Visit (Visit 2) to End of Study (Visit 7, or date of withdrawal).

Of note, patients that receive the last planned setmelanotide dose at Week 16 (Visit 6) and meet the primary endpoint, can elect to enroll in a separate extension study, Rhythm Study RM-493-022, under which auspices the patient will continue to receive setmelanotide.

### 4.2 Visit Windows

Study visits are expected to occur according to the protocol schedule ([Section 16.1](#)). Efficacy by-visit summaries and analyses will use analysis visits. Both scheduled and

unscheduled visits (including early termination visit) will be windowed based on the following analysis visit windows.

**Table 1 Analysis Visit Windows**

Analysis Visit	Target Study Day	Analysis Visit Window
(Intentionally left blank)	-56 - -1	<1*
Baseline	1	1
Week 4	29	2 - 43
Week 8	57	44 – 71
Week 12	85	72 – 99
Week 16	113	100 - 127
Week 20	141	≥ 128

\*The exception to this windowing is the height assessment completed prior to Baseline, as height assessments are not completed at Baseline visit. Visit 1 height assessments should be included in the Baseline analysis visit window.

If two or more assessments (include both scheduled and unscheduled assessments) are available for the analysis visits, then all assessments will be included in data listings and the following rules will be applied for determining the values to be used for the summaries and analyses in tables:

- Efficacy assessments: the assessment taken closest to the target study day will be used for the summaries and analyses; if two visits are equally distant to the target study day, then the more recently occurring visit will be chosen (i.e. If the target study day was 01 JAN 2021 and Visit A occurred on 27 DEC 2020 and Visit B occurred on 06 JAN 2021 (both 5 days apart from the target study day), then Visit B will be chosen).

Safety by-visit summaries and analyses will use the nominal evaluation visit, as recorded on the eCRF. Both scheduled and unscheduled visits (including early termination visit) will be windowed based on the protocol-specified windows outlined in [Section 16.1](#). If two or more assessments (include both scheduled and unscheduled assessments) are available for the visits, then all assessments will be included in data listings and the following rules will be applied for determining the values to be used for the summaries and analyses in tables:

- Safety assessments, excluding clinical laboratory tests: the scheduled visit will be used over any unscheduled visits conducted within window; otherwise, the assessment taken closest to the target study day will be used for the summaries and analyses
- Clinical laboratory tests: the scheduled visit will be used over any unscheduled visits conducted within window; otherwise, the latest assessment will be used for the summaries and analyses.

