9.5. Height

For patients ≥ 18 years of age, height needs to be measured at Screening only. For patients aged < 18 years, height is to be measured at the time points designated in the SoA ([Table 1](#)).

Height (cm) will be measured, without shoes, socks, or hats, using a wall-mounted stadiometer. All measurements will be done in triplicate at each time point and recorded to the nearest half cm.

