10.3. Statistical Analyses

A separate statistical analysis plan will be developed, which will include a more technical and detailed description of the statistical analyses described in this section. This section is a summary of the planned statistical analyses of the most important endpoints including primary and other endpoints

The primary endpoint is defined as the proportion of patients who achieve at least 5% BMI reduction from baseline, at ~16 weeks of treatment with setmelanotide. The primary statistical hypothesis will be tested with an exact binomial test at 1-sided 0.05 significant level, compared to a historical control rate of 5%. The 2-sided 90% Clopper-Pearson confidence interval will be provided.

For the primary endpoint, and all other endpoints, the last value obtained prior to the first dose of active treatment will be considered the baseline value for statistical analyses.

AEs will be coded by using the most current version of Medical Dictionary for Regulatory Activities and summarized by system organ class, preferred term, and treatment group for the number and percent of AEs reported, the number of patients reporting each AE, and the number of patients with any AE.

A by-patient AE data listing including onset and resolution dates, verbatim term, preferred term, treatment, severity, relationship to treatment, action taken, and outcome will be provided.

Safety data including laboratory evaluations and vital signs assessments will be summarized by time of collection and by treatment group. In addition, change from baseline to any post-dose values will be summarized for vital signs and clinical laboratory results. Frequency of patients with abnormal safety laboratory results will be tabulated by treatment.

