### 4.3 Baseline Definitions

For all analyses, baseline will be defined as the most recent measurement prior to the first administration of study drug, including assessments done at the Screening visit (Visit 1),

Unscheduled visits conducted prior to study treatment, and pre-treatment assessments done at the Baseline visit (Visit 2).

In general, change from baseline ( $\Delta$ ) will be calculated as the value at a given time point,  $X$ , minus the baseline value:

$$\Delta = X \text{ Value} - \text{Baseline Value}$$

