## 9.1 Primary Efficacy Endpoint

The primary endpoint is defined as the proportion of patients who achieve at least 5% BMI reduction from baseline, at ~16 weeks of treatment with setmelanotide. BMI will be calculated using patient's weight and height assessments, using the following formula:

$$BMI = \frac{kg}{m^2}$$

If needed, weight and height will first be converted into kilograms and meters, respectively. Given that body weight is collected in triplicates at each visit, weight (kg) will first be aggregated into one averaged weight per visit. Visits will then be compared against the analysis visit window (described in [Section 4.2](#)) to select the Week 16 averaged weight prior to calculating BMI and change in BMI. Patients who are  $\geq 18$  years of age will only have height measurement done at screening; the averaged triplicate

screening height will be used for the height component of the BMI calculation at each visit. Patients who are < 18 years of age will have their height measured in triplicates at most study visits. As with body weight, height will first be aggregated into one averaged height per visit and compared against the analysis visit window to select the Week 16 averaged height. Regardless of reason, if height is missing for an analysis visit, then height will be imputed using last observation carried forward (LOCF). Change ( $\Delta$ ) in BMI (%) from baseline at 16 weeks of treatment will be calculated as follows:

$$\Delta \text{ BMI } (\%) = \left( \frac{\text{Week 16 BMI} - \text{Baseline BMI}}{\text{Baseline BMI}} \right) * 100$$

An indicator variable will then be created to identify patients that have a decrease in BMI from baseline to Week 16 of 5% or more, allowing for the analysis of proportion of patients who achieve at least 5% BMI reduction.

The primary endpoint will be assessed using an exact binomial test at a 1-sided 0.05 significant level, compared to the null hypothesis proportion of 0.05 (which comes from a historical control rate of 5%). The number of and the binomial proportion of patients who achieve at least 5% BMI reduction from baseline at 16 weeks, the corresponding 2-sided 90% CI, and one-sided binomial test p-value will be presented. The Clopper-Pearson method will be used to calculate the CI. A scatter plot figure will also be created plotting each patient's percent BMI reduction from baseline to Week 16.

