### 9.3.1 Body Weight Loss

The proportion of patients (all ages) who achieve at least 5% body weight reduction from baseline, at  $\sim$ 16 weeks of treatment with setmelanotide will be assessed following similar methods as for the primary endpoint. Given that body weight is collected in triplicates at each visit, weight will first be aggregated into one averaged weight per visit. Visits will then be compared against the analysis visit window (described in [Section 4.2](#)) to select the Week 16 averaged weight prior to calculating change in body weight. Change ( $\Delta$ ) in body weight (%), in kg, from baseline at 16 weeks of treatment will be calculated as follows:

$$\Delta \text{Weight} (\%) = \left( \frac{\text{Week 16 weight} - \text{Baseline weight}}{\text{Baseline weight}} \right) * 100$$

An indicator variable will then be created to identify all patients that have a decrease in body weight from baseline to Week 16 of 5% or more, allowing for the analysis of proportion of all patients who achieve at least 5% body weight reduction.

Proportion of all patients who achieve at least 5% body weight reduction will be assessed using an exact binomial test at a 1-sided 0.05 significant level, compared to the null hypothesis proportion of 0.05. The number of and the binomial proportion of all patients who achieve at least 5% body weight reduction from baseline at 16 weeks, the corresponding 2-sided 90% CI, and one-sided binomial test p-value will be presented. The Clopper-Pearson method will be used to calculate the CI.

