### 11.5 Examination of Subgroups

To evaluate the consistency of the results of the primary and secondary efficacy analysis across different subgroups of interest, the primary analysis specified above ([Section 9.1](#)) will be repeated, stratifying for each of the following subgroups specified below:

- Age (< 18 years, 18+ years)

Additionally, to evaluate the exploratory objectives of this study in patients of different age groups, body weight loss, change from baseline in BMI, weight, and waist circumference (described in [Sections 9.3.2](#) and [9.3.3](#)) will be stratified by:

- Age (6 - < 18 years, 18+ years)
- Pediatric age (6 - < 12 years, 12 - < 18 years)

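### In growing children, baseline BMI pairs the Day 1 weight with a Screening height 14 to 56 days old, so on average pre-dose growth counts as BMI reduction on drug

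*SAP*

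**What the plan says.** The Schedule of Activities (Protocol Table 1, SAP 16.1) takes weight at Screening and at Visit 2. It takes height at Screening and then not again until Visit 3. The footnote to SAP Table 1 acknowledges this: "height assessments are not completed at Baseline visit. Visit 1 height assessments should be included in the Baseline analysis visit window". On the length of Screening, SAP 4.1 says "Can range between 56 – 14 days prior to Visit 2".

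Both documents use the last pre-dose value. SAP 4.3: "baseline will be defined as the most recent measurement prior to the first administration of study drug". Protocol 10.3: "the last value obtained prior to the first dose of active treatment will be considered the baseline value". For weight, that value is from Day 1. For height, it is from Visit 1.

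SAP 9.1 treats the age groups differently after that. Patients aged 18 or over keep one Screening height at every visit, so for them percent change in BMI equals percent change in weight. For patients under 18, visits are "compared against the analysis visit window to select the Week 16 averaged height". On precision, Protocol 9.5 says "All measurements will be done in triplicate at each time point and recorded to the nearest half cm".

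Neither document adjusts for the gap. The sensitivity analyses (per-protocol in SAP 9.1.1, optional multiple imputation in SAP 11.1 and 16.5) do not address it.

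**The concern.** The two BMI values in the primary endpoint span different intervals for their two components in patients under 18. Weight change runs over the 112 days from Day 1 to Day 113. Height change runs over 126 to 168 days, because it starts at Visit 1. Growth before the first dose makes baseline BMI too high, and the excess is credited to treatment. The error favours the drug on average, and there is no control arm in which it would cancel.

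The endpoint is a fixed 5% cut-off, so a small shift can change one child's responder status. With about 15 patients, one child is 1/15 = 6.7 percentage points of the response rate. Adults do not dilute the effect in the under-18 repeat of the primary analysis, which "will be repeated, stratifying for each of the following subgroups specified below" (SAP 11.5). The same baseline BMI also feeds the BMI z-score key secondary endpoints; the effect on that scale is not quantified here.

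**Working it through.** **The plan's own figure.** The documents give no figure for this error. The nearest is the stated power of about 90% (Protocol 10.1, SAP 3.4). The exact binomial test (5% null, one-sided 0.05, 40% target) gives 83.3% at N=10, 97.3% at N=15 and 98.4% at N=20, so 90% is not reproduced at those sizes. The point below does not depend on it.

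**Inputs from the documents.** Gap L = 14 to 56 days; 112 days from Day 1 to Day 113; 5% responder cut-off; height recorded to 0.5 cm; about 15 patients, of whom up to 10 may be aged 6 to 12.

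**Assumed inputs.** Growth velocity v and height H are not in the documents, so ranges are shown.

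**Size of the overstatement.** Pre-dose growth is g = v × L/365.25. With H the Visit 1 height, baseline BMI is overstated by (1 + g/H)² − 1. The true fall since Day 1 that is scored as 5% is 1 − 0.95 × (1 + g/H)².

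| v (cm/year) | H (cm) | L (days) | Overstatement |
|---|---|---|---|
| 0 | any | any | 0% |
| 2 | 165 | 14 / 56 | 0.09% / 0.37% |
| 5 | 160 | 14 / 56 | 0.24% / 0.96% |
| 6 | 115 | 14 / 56 | 0.40% / 1.61% |
| 6 | 130 | 56 | 1.42% |
| 8 | 115 | 56 | 2.14% |

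**Worked child (6 cm/year, 130 cm, 56 days).** g = 6 × 56/365.25 = 0.92 cm. Overstatement = (130.92/130)² − 1 = 1.42%. True fall scored as 5% = 1 − 0.95 × 1.0142 = 3.65%.

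Height at Week 16 = 130.92 + 6 × 112/365.25 = 130.92 + 1.84 = 132.76 cm. The weight loss needed to count as a responder is 1 − 0.95 × (132.76/baseline height)²:
- with the Day 1 height, 130.92 cm: 2.31%
- with the Visit 1 height, 130 cm: 0.92%

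**Rounding.** An error of 0.25 cm at 130 cm moves BMI by (130.25/130)² − 1 = 0.38%. In one child with a 14-day gap this can hide or reverse the effect. It does not remove the effect on average.

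**Where the test is sensitive (exact binomial against 5%).** At N=15, 2 responders give p=0.171 and 3 give p=0.036. At N=20, 3 give p=0.075 and 4 give p=0.016. One reclassified child decides the result only at those boundaries. At a 40% response rate and N=15, 15 × 0.40 = 6 responders are expected and 3 are needed.

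**Illustration of type I error.** Assume 10 growing children among 15 patients, 130 cm, 5 cm/year, percent BMI change normal with SD 4 to 8 points, and a true responder rate of 5% in everyone. The spurious change a = 100 × (1 − (H/(H+g))²) is 0.29 points at 14 days and 1.17 at 56 days. A child's apparent null rate becomes Φ(−1.645 + a/SD): 5.4-5.8% and 6.7-8.8%. Combining the two binomial groups, the chance of 3 or more responders rises from 0.036 to 0.041-0.047 (all gaps 14 days) or 0.060-0.098 (all gaps 56 days). With 5 growing children among 15 it is 0.039-0.041 or 0.047-0.063.

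**The case against.** The case for leaving this alone has several parts.

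- **The size rests on assumptions.** The documents give no growth rate, height or actual screening gap, and the worked child sits at the window's maximum. These are patients with hypothalamic tumours, some possibly on growth hormone replacement, so 5-6 cm/year need not apply. This stands: the figures are ranges, they start at zero, and at 14 days the effect is about the size of the rounding error.
- **Exposure is unknown.** Ten children aged 6 to 12 is a ceiling, and adults and adolescents who have stopped growing are unaffected. A child whose Week 16 height is carried forward from Screening has no mismatch, and an unscheduled pre-dose height would shorten the gap. This also stands; no number of misclassified children can be predicted.
- **The study is exploratory and the test is robust at the planned effect.** True, and it limits the harm chiefly to the estimate and the under-18 subgroup.
- **There are checks already.** SAP 9.3.1 tests the proportion "who achieve at least 5% body weight reduction from baseline" in all ages without using height, and SAP 9.3.2 plots BMI and weight for each patient. These help only in part. A gap between BMI and weight responders also contains real growth after Day 1, so it cannot isolate the pre-dose part.
- **Growth after Day 1 matters more.** In the worked child it lowers the weight loss needed from 5% to 2.31%, or 2.69 points, against 1.39 points for the pre-dose part. Correct, but that follows from choosing raw BMI as the endpoint and is a separate matter. Growth before the first dose cannot belong to the treatment period on any reading.
- **Interpolating height would mostly reflect rounding.** This does not hold. The interpolated Day 1 height is a weighted average of the Visit 1 and Visit 3 triplicate means, with weight L/(L + 28) on Visit 3: about 1/3 at 14 days and 2/3 at 56 days. Its rounding error is generally no larger than that of the Visit 1 height used now.
- **An amendment would come late.** The SAP rests on protocol version 2.0 of 9 September 2021, and the estimated last completion is 31 March 2022. Counting back 140 days puts the last Day 1 near mid-November 2021, or near 9 December if that patient leaves at Visit 6 (112 days). This stands, and it makes the sensitivity analysis the main remedy.

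**Conclusion.** The concern holds. The schedule and the SAP footnote together produce a baseline BMI whose height predates its weight by 14 to 56 days in patients under 18. In a growing child the direction is fixed by algebra and favours the drug on average, though not in every child. With growth of 5-6 cm/year and heights of 115-160 cm, both assumed, the overstatement is 0.24-0.40% at the shortest gap and 0.96-1.61% at the longest. It is zero without growth and 2.14% in the extreme case shown.

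This does not threaten the primary test if the response rate is near 40%. It can inflate the reported response rate and the under-18 result. It could decide the test only when the responder count is at the rejection boundary. The plan should correct it, but it does not invalidate the trial.

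**What to change.** **Patients under 18 not yet at Visit 2.** Add a triplicate pre-dose height at Visit 2 to the Schedule of Activities. Amend the SAP Table 1 footnote so that this is the baseline height, with the Visit 1 height only as a fallback. SAP 4.3 already selects the most recent pre-dose value and needs no change.

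**Patients under 18 already past Visit 2.** Keep the primary analysis as specified, because a baseline built on the on-treatment Visit 3 height would conflict with Protocol 10.3. Add a sensitivity analysis with Day 1 height interpolated linearly between Visit 1 and Visit 3. Report the response rate, the exact confidence interval and the number of children whose responder status changes, overall and for those under 18.

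**Cost.** The extra height takes a few minutes at a visit the child already attends, but the schedule change needs a protocol amendment and IRB approval (Protocol Appendix 7). If few patients remain to be enrolled, the sensitivity analysis alone is the cheap option: one extra table and no new data. The response rate may come out slightly lower.
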